##### **4.2 Subgroups**

The primary and secondary endpoints will be summarized in the subgroups defined by number of prior treatment failures (1, 2, and 3 or more treatment failures) for the traditional sites only.

The subgroups will be re-examined for appropriateness and may be re-categorized (due to small sample size, for example, if there are < 10% of subjects within a subgroup) before unblinding.

## **5. Definitions**

### **5.1 Definition of Terms Included in Study Endpoints**

#### **5.1.1 Efficacy Endpoints Based on Daily Data Collection**

The eDiary collects headache events (including start and stop time, pain features, symptoms, and severity), aura events (including start and stop time), and acute headache medications (including taken time) in 3 independent modules. The eDiary design includes optional any-time diaries and a mandatory evening diary from 5:00:00 pm to 11:59:59 pm (local time) each day for data collection.

#### **Acute Headache Medication (AHM)**

Acute headache medications include following categories collected in the eDiary:

- Triptan-based migraine medications
- Ergotamine-based migraine medications
- Non-opioid acute headache medications
- Non-opioid butalbital containing medications
- Opioid-containing acute headache medications
- Opioid-containing butalbital containing medications

#### **Acute Migraine-specific Medication (AMSM)**

A subset of acute headache medication consisting of triptan-based migraine medications and ergotamine-based migraine medications

#### **Qualified Headache**

A qualified headache is defined as

- A headache of duration  $\geq 30$  minutes
- A headache with acute headache medications (migraine-specific or not) taken during the headache (start time and end time inclusive) with any length of duration
- Acute migraine-specific medications taken during an aura (start and end time inclusive)

#### **Headache Day**

A calendar day (00:00 to 23:59) in which the subject experiences  $\geq 1$  qualified headache

### **Headache Pain Intensity**

Worst or peak pain intensity collected on a headache ranges from 0 (no pain) to 10 with a higher score indicating more severe pain. Pain intensity are categorized into mild (1 to 3), moderate (4 to 6), and severe (7 to 10).

### **Qualified Migraine Headache**

A qualified migraine headache should meet at least one of the following criteria:

- A headache of duration  $\geq 30$  minutes, and meeting  $\geq 1$  of the following criteria (a and/or b):
  - a)  $\geq 2$  of the following pain features:
    - Unilateral
    - Throbbing
    - Moderate to severe (ie, headache pain intensity  $\geq 4$ )
    - Exacerbated with exercise/physical activity
  - b)  $\geq 1$  of the following associated symptoms:
    - Nausea
    - Vomiting
    - Photophobia and phonophobia
- A headache with acute migraine-specific medications taken during the headache (start time and end time inclusively) regardless of the headache duration, pain features, and associated symptoms
- Acute migraine-specific medications taken during aura

### **Migraine Day**

A calendar day (00:00 to 23:59) in which the subject experiences  $\geq 1$  qualified migraine headache.

### **Diary Day**

A calendar day (00:00 to 23:59) with complete headache, aura, and acute headache medication data recorded in the eDiary device.

### **Information Day**

A calendar day (00:00 to 23:59) which is either a diary day or a headache day that can be derived based on available information.

### **Monthly Migraine Days (MMD)**

Number of migraine days during one monthly interval as defined below.

Number of Diary Days in a Monthly Interval	Monthly Migraine Days
• ≥ 14 days	Prorate to 28-day equivalent without rounding as follows:  $\frac{\text{Number of observed migraine days within each monthly interval}}{\text{Number of diary days within each monthly interval}} \times 28$
• < 14 days	Set to missing

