**Monthly Headache Days (MHD)**

Number of headache days during one monthly interval as defined below.

Number of Diary Days in a Monthly Interval	Monthly Headache Days
• ≥ 14 days	Prorate to 28-day equivalent without rounding as follows:  $\frac{\text{Number of observed headache days within each monthly interval}}{\text{Number of information days within each monthly interval}} \times 28$
• < 14 days	Set to missing

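### The SAP counts migraines recorded on incomplete diary days in the numerator of monthly migraine days but not in its denominator

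*SAP*

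**What the plan says.** SAP 5.1.1 sets the MMD denominator as "Number of diary days within each monthly interval". The numerator is the observed migraine days in the interval, with no further condition, and the ratio is scaled to 28 days when there are at least 14 diary days.

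The definitions behind the two parts differ:

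- A migraine day is "A calendar day (00:00 to 23:59) in which the subject experiences" at least one qualified migraine headache. Diary completeness is not required.
- A diary day is one "with complete headache, aura, and acute headache medication data recorded in the eDiary device".
- An information day is one "which is either a diary day or a headache day that can be derived based on available information". The MHD denominator is "Number of information days within each monthly interval".

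The eDiary collects headache, aura and medication "in 3 independent modules", with optional any-time entries as well as a mandatory evening diary. SAP 8.3 repeats the proration, refers back to 5.1.1 and names no denominator of its own.

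**The concern.** A partly recorded day can still be a migraine day. One route to a qualified migraine is "A headache with acute migraine-specific medications taken during the headache", whatever the duration, features or symptoms; another is such a drug taken during aura. Either can be on file while another module for that day is incomplete. The day then counts above the line and not below it.

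The SAP foresaw partial days, because it created the information day for headaches and used it for MHD. The same record is thus handled consistently for MHD and inconsistently for MMD. Every qualified migraine headache is also a qualified headache, so MMD should never exceed MHD, yet the formulas allow it.

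At stake is a coherent, reproducible derivation of a confirmatory endpoint. A programmer who follows the text and one who assumes that the numerator means diary days only would produce different values.

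**Working it through.** **The plan's own figure.** SAP Table 3-1 assumes an MMD difference of -2.0, SD 3.4, 120 per group and two-sided alpha 0.05. The standard error is 3.4 × √(2/120) = 0.439, and 2.0/0.439 = 4.56. Power is Φ(4.56 - 1.96) = 0.995, which reproduces the stated value above 99%.

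**Formulas.** Let D = diary days, m = migraine days on diary days, and k = migraine days recorded on other days.

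- SAP: 28(m + k)/D
- Diary days in both parts: 28m/D
- Matched (the k days also in the denominator): 28(m + k)/(D + k)

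The SAP value exceeds the diary-day value by 28k/D and is (1 + k/D) times the matched value. If there are no other headaches, MHD equals the matched value.

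**Single months (assumed counts).**

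| D | m | k | SAP | Matched | Diary days only |
|---|---|---|---|---|---|
| 25 | 7 | 1 | 8.96 | 8.62 | 7.84 |
| 21 | 6 | 2 | 10.67 | 9.74 | 8.00 |
| 14 | 5 | 2 | 14.00 | 12.25 | 10.00 |

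In the second row, 8/21 × 28 = 10.67 is the MMD, and 8/23 × 28 = 9.74 is the MHD when there are no other headaches.

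**Averages when completeness is unrelated to migraine.** Let T = true MMD, c = share of days that are diary days, and q = share of migraines on incomplete days that are still recorded. The documents give neither c nor q. Then m = Tc, k = T(1 - c)q and D = 28c, so the SAP value is T[1 + (1 - c)q/c] and the diary-day value is exactly T. For assumed arm means of 8 and 6 (true difference -2.00):

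| c | q | SAP | Matched | Diary days only |
|---|---|---|---|---|
| 1 | any | -2.00 | -2.00 | -2.00 |
| 0.9 | 0.25 | -2.06 | -2.03 | -2.00 |
| 0.75 | 0.25 | -2.17 | -2.08 | -2.00 |
| 0.75 | 0.5 | -2.33 | -2.15 | -2.00 |

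In the last row, a true mean of 8 becomes 9.33 by the SAP rule and 8.91 by the matched rule. The matched rule removes only 0.42 of the 1.33-day excess, because incomplete days enter only when a migraine was recorded.

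**When migraine itself makes the diary incomplete.** Assume that 60% of migraine days and 81% of other days are diary days, with true MMD 8. Then m = 4.8, D = 4.8 + 20 × 0.81 = 21 and k = 3.2q.

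| q | SAP | Matched | Diary days only |
|---|---|---|---|
| 0.25 | 7.47 | 7.19 | 6.40 |
| 0.5 | 8.53 | 7.93 | 6.40 |
| 0.75 | 9.60 | 8.62 | 6.40 |

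No rule is closest to the truth in every case.

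**The case against.** The best defence is that the numerator was meant to cover diary days only. Migraine status needs more data than headache status. A headache qualifies on 30 minutes' duration, or as "A headache with acute headache medications (migraine-specific or not) taken during the headache", whereas migraine needs features, symptoms or a migraine-specific drug. That could explain complete days for MMD and information days for MHD. It is plausible, but the SAP states it nowhere and the migraine-day definition has no such limit. If it was the intention, one sentence settles the point.

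The second defence is that no harm is shown. The evening diary is mandatory, and Protocol 6.3 requires at least 75% eDiary compliance for entry. Completeness rules may also sit in the data management plan, which is not available here. When completeness is unrelated to migraine and equal across arms, the SAP rule multiplies both arm means by the same factor, so it rescales a difference and does not create one. MHD is not an endpoint in SAP Tables 9-1 to 9-3; SAP 9.4 lists it only as a baseline characteristic. All of this stands, and it limits the severity.

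The third is that the SAP value is sometimes nearest the truth (7.47 against a true 8 in the last table). That is correct, but it comes from two errors offsetting each other.

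**Conclusion.** The mismatch is in the text. As written, a migraine recorded on an incomplete day raises MMD by 28/D with no matching denominator day, and MMD can exceed MHD. Severity is minor to moderate. Under the assumed rates with c below 1, the SAP rule moves a true difference of -2.0 to between -2.06 and -2.33, which is 0.03 to 0.18 days from the matched rule. With complete diaries the effect is zero.

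A reader might infer more than the documents support:

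- **A biased comparison or inflated type 1 error.** This would need recording to differ between blinded arms, and nothing in the documents indicates that. If it did differ, the shift could go either way. With assumed true means of 6 on placebo and 4 on erenumab and q = 1, c of 0.8 on placebo and 0.9 on erenumab gives -3.06; the reverse gives -1.67.
- **MMD always above the truth.** The last table shows otherwise.
- **MMD above 28 as a practical problem.** The formula permits it (15/14 × 28 = 30), but only with 15 recorded migraine days in a month with 14 diary days, in subjects enrolled with fewer than 15.
- **A conflict with the protocol.** Protocol 10.2.4 prorates on days with information available but does not define them, so no contradiction can be shown.

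The primary endpoint and the planned MMD power are not in question.

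**What to change.** Before unblinding, amend SAP 5.1.1 so that both parts of MMD refer to the same days: count migraine days that fall on diary days, divide by diary days, and multiply by 28. Keep the 14-diary-day minimum, leave MHD unchanged, and have SAP 8.3 name the denominators. MMD then cannot exceed MHD. Headache days on diary days are at least as many as migraine days there, and MHD adds any further headache days to both its parts, which cannot lower the ratio.

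Add one sensitivity derivation: all recorded migraine days over diary days plus those non-diary days whose migraine status can be derived. Plain information days would not serve, because a headache that cannot be classified would count as non-migraine. With D = 21, 6 migraine days and 2 such headache days, 6/21 × 28 = 8.00 would become 6/23 × 28 = 7.30.

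The cost is a few lines of programming and one table. The diary-day rule discards migraines recorded on incomplete days and reads low if migraine causes the incompleteness (6.40 against a true 8 in the assumed case). The sensitivity derivation would show this, although it can itself read high (8.91 against 8 at c = 0.75, q = 0.5).

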**Monthly Headache Days (MHD)**

Number of headache days during one monthly interval as defined below.

Number of Diary Days in a Monthly Interval	Monthly Headache Days
• ≥ 14 days	Prorate to 28-day equivalent without rounding as follows:  $\frac{\text{Number of observed headache days within each monthly interval}}{\text{Number of information days within each monthly interval}} \times 28$
• < 14 days	Set to missing

**5.1.2 Efficacy Endpoints Based on Weekly Collection**

**Work Productivity and Activity Impairment (WPAI) Questionnaire**

In the WPAI-Migraine questionnaire, subjects are asked 6 questions about work and activity impairment due to their migraine, including hours worked and hours missed in the last 7 days. The questionnaire will be collected weekly during baseline and post-baseline.

The weekly percent work impairment score is calculated based on questions 2, 4 and 5. Higher score indicates worse outcome.

The monthly percent work impairment equals to the arithmetic mean of the observed weekly percent work impairment scores over the monthly interval, if the number of weekly scores during baseline period or each of the monthly interval during post-baseline is ≥ 2. Otherwise, monthly measurement will be set to missing.

**5.1.3 Efficacy Endpoints Based on Monthly Collection**

**Modified Migraine Disability Assessment (Modified MIDAS)**

The modified MIDAS Questionnaire is a 5-item self-administered questionnaire that assesses in the past month the number of productive days lost in 2 settings (workplace and home) and disability in family, social, and leisure activities. Absenteeism score is

the response from question 1, and presenteeism score is the response from question 2. The total score ranging from 0 to 93 is the sum of the responses to all 5 items. Higher scores indicate worse outcome. The modified MIDAS will be collected monthly during baseline and post-baseline.

### **Migraine Functional Impact Questionnaire (MFIQ)**

The MFIQ version 2.0 is a self-administered 26-item instrument measuring the impact of migraine on broader functioning including 4 domains: Impact on Physical Functioning (5 items), Impact on Usual Activities (10 items), Impact on Social Functioning (5 items), and Impact on Emotional Functioning (5 items). In addition, there is 1 stand-alone global item assessing the overall impact on usual activities. Subjects respond to items using a 5-point scale assigned scores from 1 to 5, with 5 representing the greatest burden. Each domain score will be calculated as the sum of the item responses and the sum will be rescaled to a 0 to 100 scale, with higher scores representing greater burden. The recall period is the past 7 days and will be collected monthly during baseline and post-baseline.

#### **5.1.4 Efficacy Endpoints Collected at Specific Visits**

### **Patient Health Questionnaire (PHQ-9)**

The Patient Health Questionnaire (PHQ) is a 9-question, self-administered instrument for screening, diagnosing, monitoring, and measuring the severity of depression. Each item has response as “0” (not at all) to “3” (nearly every day). The score is calculated as the sum of the 9 item responses, ranging from 0 to 27 with higher score representing severer depression. PHQ-9 will be collected at baseline and at months 1, 3 and 6 post-baseline.

### **Generalized Anxiety Disorder 7-item Scale Questionnaire (GAD-7)**

The GAD-7 is a self-administered 7-item instrument to identify probable cases of GAD along with measuring anxiety symptom severity. Responders are asked to rate the frequency of anxiety symptoms in the last 2 weeks on a Likert scale ranging from 0 (not at all) to 3 (nearly every day). Items are summed to provide a total score, ranging from 0 to 21 with higher score indicating severer symptoms. GAD-7 will be collected at baseline and at months 1, 3 and 6 post-baseline.

### **Pittsburgh Sleep Quality Index (PSQI)**

The PSQI is a self-reported questionnaire that assesses sleep quality over a 1-month time interval. The measure consists of 19 individual items, creating 7 components that produce 1 global score. Each component scored 0 (better) to 3 (worse). The global score is the sum of each component score, ranging from 0 to 21 with higher score indicating worse sleep quality. PSQI will be collected at baseline and at months 1, 3 and 6 post-baseline.

### **Epworth Sleepiness Scale (ESS)**

The ESS is a self-administered questionnaire with 8 questions designed to assess daytime sleepiness. Respondents are asked to rate, on a 4-point scale (0 to 3), their usual chances of dozing off or falling asleep while engaged in 8 different activities. The ESS score (the sum of 8 item scores, 0 to 3) can range from 0 to 24 with higher ESS scores indicating higher average sleep propensity (ASP) in daily life, or “daytime sleepiness”. ESS will be collected at baseline and at months 1, 3 and 6 post-baseline.

### **Patient Satisfaction at Work**

To better understand impact of depression, anxiety, sleepiness, and inability to concentrate on work productivity, subjects will be asked to complete the following questions on a 10-point scale with higher score representing severer impacts:

- How much does your depressed mood, as a result of your migraines, impact your ability to function at work? **Scale**, 0 = no impact to 10 = severely impacts
- How much does your anxiety, as a result of your migraines, impact your ability to function at work? **Scale**, 0 = no impact to 10 = severely impacts
- How much does your sleepiness, as a result of your migraines, impact your ability to function at work? **Scale**, 0 = no impact to 10 = severely impacts
- How much does your inability to concentrate, as a result of your migraines, impact your ability to function at work? **Scale**, 0 = no impact to 10 = severely impacts
- How would you rate your overall satisfaction with your productivity at work? **Scale**, 0 = as dissatisfied as you can imagine to 10 = as satisfied as you can imagine

These questions are not part of a validated questionnaire and will be scored individually. The recall period is the past month. Patient satisfaction at work will be collected at baseline and at months 1, 3 and 6 post-baseline.

### **Psychomotor Vigilance Task (PVT)**

Psychomotor Vigilance Task is a sustained-attention, reaction-timed task that measures the speed with which a subject responds to a visual stimulus. Mean reaction time in millisecond, number of lapses and errors will be calculated from the individual elapsed time recordings during the 10-minute session. PVT will be collected at baseline and at months 1, 3 and 6 post-baseline.

Subjects enrolled as part of the DCTS will not complete this assessment.

### **Health Resource Utilization (HRU) Questionnaire**

The questionnaire is designed to collect data on HRU. Specifically, the aim is to capture frequency of migraine-related hospitalizations and outpatient visits including emergency department visits, urgent care visits, and other clinical visits. The recall period for the HRU questionnaire is 24 weeks, and the HRU questionnaire will be administered on day 1, and week 24 of the DBTP. The questionnaire assessed at the early termination visit before week 24 should only include HRU recalled since the previous assessment at day 1 to avoid collecting duplicate information. HRU will be collected at baseline and at month 6 post-baseline.

#### **5.1.5 Efficacy Endpoints Based on Wearable Device Collection**

Physical activity will be measured continuously by a wearable device (accelerometer) from baseline through the end of study except when recharging. Analysis of physical activity endpoints will only include activity data collected while subjects are wearing the device and are awake (not sleeping), ie, during wear and awake time.

#### **Valid Day**

A valid day is defined when there are at least 10 hours (600 minutes) of wear and awake time per calendar day (00:00 to 23:59). Analysis of physical activity endpoints will only include activity data collected during wear and awake time on valid days.

#### **Physical Activity Category**

Physical activity level can be defined in the following 6 categories:

- Sedentary
- Light
- Lifestyle

- Moderate
- Vigorous
- Very vigorous

Note: The raw data will include total minutes of wear and awake time corresponding to each physical activity category per calendar day.

### **Total Minutes of Wear and Awake Time in a Valid Day**

Sum of total minutes of wear and awake time for each of the 6 physical activity categories in a valid day

### **Daily Proportion of Time Spent in Each Physical Activity Category per Valid Day**

$$\frac{\text{Total minutes of wear and awake time spent in each physical activity category in a valid day}}{\text{Total minutes of wear and awake time in a valid day}}$$

Note: Since total minutes of wear and awake time vary daily, daily proportion is meant to normalize the *daily* physical activity level before calculating the *monthly* average.

### **Monthly Average of Daily Proportion of Time Spent in Each Physical Activity Category on Valid Days**

Number of Valid Days in a Monthly Interval	Monthly average of daily proportion of time spent in each physical activity category
• $\geq 14$ days	$\frac{\text{Sum of (daily proportion of time spent in each physical activity category)}}{\text{Total number of valid days in a month}}$
• $< 14$ days	Set to missing

### **Sleep Period**

A sleep period is defined to be at least 160 minutes long that starts when 5 consecutive minutes marked as “sleep” and ends once there are 10 consecutive minutes marked as “awake”.

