### **Sleep Efficiency**

Sleep efficiency is the total number of minutes marked as sleep during the total length of the sleep period in minutes.

$$\frac{\text{sleep time in minutes}}{\text{Total minutes of sleep period (sleep minutes + awake minutes)}}$$

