## **5.4 Study Time Intervals**

### **5.4.1 Monthly Intervals for Efficacy Endpoints Derived From Daily, Weekly, or Wearable Data Collection**

The (4-week) monthly intervals for efficacy endpoints derived from daily eDiary collection, weekly collection for WPAI, or wearable device (physical activity data only) will be determined based on each subject's monthly IP dosing dates. When an IP is

missed, discontinued, or no longer required, a 28-day monthly interval will be used. Any eDiary or wearable data occurring after EOS date will not be included in the analysis.

Applicable efficacy endpoints utilizing the monthly intervals in [Table 5-1](#) include:

- Monthly migraine days (MMD)
- Monthly headache days (MHD)
- Monthly percent work impairment as measured by WPAI
- Monthly average daily proportion of time spent in each physical activity category: sedentary, light, lifestyle, moderate, vigorous, and very vigorous

**Table 5-1. Monthly Intervals for Efficacy Endpoints Derived From Daily, Weekly, or Physical Activity Wearable Data Collection**

Study Period	Assessment Timepoint	Monthly Interval	
		Start Date (Day) a	End Date (Day) b
Baseline Period	Baseline	Date of device ready for entry c	Day prior to study day 1
Double-blind Treatment Period	Week 4 (Month 1)	Study Day 1	Week 4 dose date – 1
	Week 8 (Month 2)	Week 4 dose date	Week 8 dose date – 1
	Week 12 (Month 3)	Week 8 dose date	Week 12 dose date – 1
	Week 16 (Month 4)	Week 12 dose date	Week 16 dose date – 1
	Week 20 (Month 5)	Week 16 dose date	Week 20 dose date – 1
	Week 24 (Month 6)	Week 20 dose date	Week 20 dose date + 27

a Start Date (Day) = End date (day) of previous monthly interval + 1 if IP dose date is not available

b End Date (Day) = Start date (day) of current monthly interval + 27 if IP dose date is not available

c For physical activity wearable data, Baseline Start Date (day) is defined as Max (Earliest valid activity date, week -4 visit date)

Sleep associated endpoints from each sleep period will utilize the monthly intervals defined in [Table 5-2](#) based on the sleep start date/time.

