**Table 9-3. Exploratory Efficacy Endpoint Summary Table**

Endpoint	Primary Summary and Analysis Method	Sensitivity Analysis
Endpoints defined as change from baseline at each monthly assessment time point c	
 
1. Summary statistics by visit using observed data
 
2. Least squares means from a generalized linear mixed effect model including treatment group, scheduled visit, interaction of treatment group and scheduled visit and baseline value using observed data
 
3. Test treatment difference (AMG 334 – Placebo) from the model in #2.
 
	
Occurrence of at least 1 migraine-related hospitalization or outpatient HRU during the 6-month DBTP d	
 
1. Summary statistics using observed data at month 6
 
	

Page 2 of 2

a The same analysis methods will be applied to the endpoints:

Change from baseline in mean overall impact on usual activities global item score over months 4, 5, and 6 of the 6-month DBTP, as measured by MFIQ.

b The same analysis methods will be applied to the following endpoints at months 1, 3, and 6:

PHQ-9 total score,  
 GAD-7 total score,  
 PSQI total score,  
 ESS total score,  
 Patient satisfaction at work,  
 Mean reaction time, number of lapses, and number of errors as measured by PVT.

c The same analysis methods will be applied to the following endpoints at all 6 months:

Change from baseline in monthly average daily proportion of time spent in each physical activity category: sedentary, light, lifestyle, moderate, vigorous, and very vigorous,  
 Change from baseline in monthly average sleep efficiency.

d The same analysis method will be applied to all HRU endpoints.

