### **9.5.2 Analyses of Exploratory Efficacy Endpoints**

The primary analysis of the exploratory efficacy endpoints will be conducted in the same way as that for the primary and secondary endpoints as outlined in [Table 9-3](#). No sensitivity analyses will be performed for the exploratory efficacy endpoints.

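### Wearable sleep efficiency counts at most the first 10 minutes of a long awakening and gives no value for nights without a 160-minute bout (exploratory endpoint, minor)

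*SAP*

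**What the plan says.** SAP 5.1.5 builds the endpoint in two steps.

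- The period comes first: "A sleep period is defined to be at least 160 minutes long". It opens with a run of 5 minutes scored asleep and closes at a run of 10 minutes scored awake.
- The ratio follows, in these words: "Sleep efficiency is the total number of minutes marked as sleep during the total length of the sleep period in minutes". The formula below that sentence divides sleep minutes by the sleep plus awake minutes of the period.

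SAP 5.4.1 keeps the single period as the unit and places it in a month by its start time: "Sleep associated endpoints from each sleep period will utilize the monthly intervals defined in" a separate table, numbered 5-2. Footnote c of Table 9-3 then lists "Change from baseline in monthly average sleep efficiency" among the endpoints modelled at all 6 months. SAP 9.5.2 adds: "No sensitivity analyses will be performed for the exploratory efficacy endpoints".

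Neither document says how periods of one night are combined, what happens to stretches under 160 minutes, how a night without a qualifying period is reported, whether the closing 10 awake minutes belong to the period, or how many nights a monthly average needs. For physical activity from the same device, SAP 5.1.5 sets the monthly value to missing below 14 valid days.

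**The concern.** Sleep efficiency is normally meant to fall when someone lies awake for a long time in the night. Under this rule a long awakening does not lower the ratio by its length. It closes one period and, if sleep resumes, another may open and be scored separately. If none of the resulting bouts reaches 160 minutes, the night contributes nothing.

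Two things are at stake. First, if erenumab shortens or prevents awakenings of 10 minutes or more, most of that benefit cannot appear in the endpoint. Second, whether a night has a value depends on how sleep is broken up, which treatment could itself influence, and no planned output would show the number of nights lost in each arm. The protocol rationale (Section 3.1) cites the impact of migraine on sleep quality and quantity, and subjects wear the device throughout the study partly to monitor sleep.

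**Working it through.** **Inputs.** From SAP 5.1.5: start at 5 consecutive sleep minutes, end at 10 consecutive awake minutes, keep the period if it is at least 160 minutes, efficiency = sleep / (sleep + awake) within the period. The SAP states no figure to reproduce, so the rule was applied minute by minute to constructed 480-minute nights. S is sleep and W is awake, in minutes. Because the SAP does not place the closing 10 awake minutes, both readings are shown. Where a night yields two periods, they are averaged with equal weight, which is also an assumption.

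| Night | Over all 480 min | SAP, closing minutes out | SAP, closing minutes in |
|---|---|---|---|
| 180 S, 120 W, 180 S | 360/480 = 75.0% | 180/180 twice = 100% | 180/190 = 94.7% and 100%; mean 97.4% |
| 210 S, 60 W, 210 S | 420/480 = 87.5% | 100% | 210/220 = 95.5% and 100%; mean 97.7% |
| three 140 S, two 30 W | 420/480 = 87.5% | bouts of 140: no value | bouts of 150, 150, 140: no value |
| five 80 S, four 20 W | 400/480 = 83.3% | bouts of 80: no value | longest bout 90: no value |
| three 150 S, two 15 W | 450/480 = 93.8% | bouts of 150: no value | 150/160 = 93.8% twice, third bout dropped |
| 20 S and 9 W, 16 times, then 16 S | 336/480 = 70.0% | 70.0% | 70.0% |
| 170 S, 310 W | 170/480 = 35.4% | 170/170 = 100% | 170/180 = 94.4% |

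Rows 1 and 2 show the insensitivity: doubling the awakening from 60 to 120 minutes lowers whole-night efficiency by 12.5 points and the SAP value by 0 or about 0.3. Rows 3 and 4 show nights that drop out under either reading. Row 6 shows that short awakenings are handled properly. Rows 5 and 7 show that dropout follows the spacing of bouts and not how bad the night was.

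**Illustration with assumed inputs.** None of these inputs comes from the documents. Each setting has 4,000 nights of 480 minutes, with a Poisson number of long awakenings (10 minutes plus an exponential time with mean 25) and about 8 brief ones of 1 to 4 minutes; closing minutes are excluded.

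| Long awakenings per night (mean) | Whole-night efficiency | SAP efficiency | Nights with no value |
|---|---|---|---|
| 0.5 | 92.5% | 96.0% | 0.4% |
| 1 | 89.5% | 96.0% | 2.2% |
| 2 | 83.7% | 96.1% | 9.5% |
| 3 | 78.0% | 96.1% | 21.2% |
| 4 | 73.0% | 96.1% | 33.1% |

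Counting the closing minutes softens this without removing it. In a variant with about 10 brief awakenings and a mean exponential time of 15 minutes, the SAP value falls from about 94% to about 92% while whole-night efficiency falls from 92.5% to about 78%. About 27% of nights then have no value at the highest setting.

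**The case against.** The best case for leaving the rule alone has five parts.

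- **The endpoint is peripheral.** Sleep efficiency is absent from the objectives and endpoints tables of both documents. It appears as an endpoint only in Table 9-3 footnote c, outside the testing sequence, and the same rule applies to both blinded arms. This stands and sets the severity.
- **Sleep is measured elsewhere.** The PSQI, whose components include habitual sleep efficiency and sleep disturbances, and the ESS are collected at baseline and months 1, 3 and 6. A reader might infer that a null result here would be taken as no effect on sleep at all. The plan does not support that. Both instruments are self-reported, however, so this remains the only device-based sleep endpoint in the efficacy tables.
- **Broad statements fail.** A reader might infer that long awakenings are never counted, or that the worst nights are the missing ones. Up to 10 minutes of each awakening may count. The 35.4% night gets a near-perfect score, while the 93.8% night can be dropped.
- **The simulation has its result built in.** Only awakenings of at least 10 minutes were varied, so a nearly flat SAP value had to follow. It illustrates size under assumptions and does not predict this trial. It would be wrong to infer that any effect on sleep will vanish, because a change in awakenings under 10 minutes would be visible.
- **The 160-minute minimum has a purpose.** It keeps naps out. With a fixed noon-to-noon window, a 30-minute nap at 14:00 followed by unbroken sleep from 23:00 to 07:00 would score 510/1020 = 50%. A remedy must not introduce that error.

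None of this changes the arithmetic in the first, third and fourth rows of the first table, and no section of either document rejoins the periods of one night.

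**Conclusion.** The concern holds in a limited form. Because efficiency is scored within periods that close at 10 awake minutes, it is insensitive to a treatment effect on long awakenings. A night at 75% scores 100% or about 97%, and a night at 87.5% with two evenly spaced 30-minute awakenings has no value under either reading. Nights drop out when no bout reaches 160 minutes; other nights with long awakenings score near 100%. The monthly average also has no minimum number of nights.

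The fixed examples rest only on the SAP rule, the two readings of the closing minutes and equal weighting of periods. How far the endpoint would be attenuated in this trial depends on awakening patterns that the documents do not give. Severity is minor: one exploratory endpoint is affected, and the primary and secondary analyses, the error control and the sample size are not.

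**What to change.** In SAP 5.1.5, before unblinding:

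1. Derive one value per main sleep episode. Join bouts separated by less than a stated maximum gap, for example 3 hours, so that daytime naps stay separate. Apply the 160-minute minimum to the joined episode, not to each bout.
2. Put every awake minute between first onset and final wake in the denominator, and say whether the closing 10 minutes count.
3. Require at least 14 nights per monthly interval, matching the activity rule.
4. Report the number of nights without a value by arm.
5. Keep the current per-period value as a supplementary output, labelled within-period efficiency.

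With a 3-hour gap and the closing minutes left out, the 120-minute example returns 360/480 = 75.0%, the two-awakening example 420/480 = 87.5% and the four-awakening example 400/480 = 83.3%. The nap example is unharmed: the gap from 14:30 to 23:00 is 8.5 hours, so the nap is not joined and the night scores 480/480 = 100%.

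Costs and limits: the change needs SAP wording and reprogramming. The gap length is a convention and needs care for shift workers. Minute-level sleep/awake marks must be obtained from the device data. The period rule itself presupposes them, but SAP 5.1.5 describes the raw activity data as daily totals and SAP 8.2 leaves transfer details to other plans, so availability should be confirmed. Waking before first onset or after the last bout stays uncounted (the 170-minute example would still score 100%), because the documents define no time in bed.
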